# 2.4.1.3 Additional analyses of baseline characteristics

Additional analyses of demographics and baseline characteristics on selected endpoints will also be replicated in the subgroup of patients of the region North America, overall and in the fenofibrate stratum as per IVRS.

#### 2.4.2 Prior or concomitant medications

The prior, concomitant and post-treatment medications will be presented for the safety population. Summaries will be repeated within each actual stratum defined by the actually received treatment (for strata with at least 10% of patients).

Medications will be coded according to the WHO-DD dictionary, considering the first digit of the anatomic therapeutical chemical (ATC) class (anatomic category) and the first 3 digits of the ATC class (therapeutic category). All ATC codes corresponding to a medication will be summarized by treatment group, and patients will be counted once in each ATC category (anatomic or

therapeutic) linked to the medication. Therefore patients may be counted several times for the same medication.

The table for prior medications will be sorted by decreasing frequency of ATC followed by all other therapeutic classes based on the overall incidence across treatment groups. In case of equal frequency regarding ATCs (anatomic or therapeutic), alphabetical order will be used.

The tables for concomitant and post-treatment medications will be sorted by decreasing frequency of ATC followed by all other therapeutic classes based on the incidence in the alirocumab group. In case of equal frequency regarding ATCs (anatomic or therapeutic), alphabetical order will be used.

In addition, the following specific medications will be summarized:

- Concomitant CV drugs will be summarized by treatment group by chemical class and standardized medication name, and by therapeutic class and standardized medication name. The tables will be sorted by decreasing frequency of chemical or therapeutic class and then of standardized medication based on the incidence in the alirocumab group.
- LMTs (statins and other LMTs, including nutraceutical products that may affect lipids) will be described by treatment group, pre-specified categories and standardized medication name. The table for prior LMTs will be sorted by decreasing frequency of standardized medication name based on the overall incidence across treatment groups within categories. The tables for concomitant and post-treatment LMTs will be sorted by decreasing frequency of standardized medication name based on the incidence in the alirocumab group.

For LMTs at randomization the following will be described:

- o Proportion of patients with any statin
- o Proportion of patients according to highest intensity of statin therapies (high intensity, moderate intensity, low intensity) according to the following table:

High-intensity statin therapy	Moderate-intensity statin therapy	Low-intensity statin therapy
Atorvastatin 40-80 mg	Atorvastatin 10-20 mg	Fluvastatin 20-40 mg
Rosuvastatin 20-40 mg	Fluvastatin 40 mg BID	Lovastatin 20 mg
Simvastatin 80 mg	Fluvastatin XL 80 mg	Pitavastatin 1 mg
	Lovastatin 40 mg	Pravastatin 10-20 mg
	Pitavastatin 2-4 mg	Simvastatin 10 mg
	Pravastatin 10-20 mg	
	Rosuvastatin 5-10 mg	
	Simvastatin 20-40 mg	

Regarding doses not included in this table:

- A statin dose that falls in between two intensity classes will be counted in the class of lowest intensity (i.e. pravastatin 30 mg will be counted as low intensity, atorvastatin 30 mg will be counted as moderate intensity).
- A statin dose under the lower threshold of low intensity will be counted as low intensity (i.e., lovavastatin 10 mg will be counted as low intensity).
- A statin dose above the higher threshold of high intensity will be counted as high intensity (i.e., rosuvastatin 80 mg will be counted as high intensity).

Simvastatin  $\geq 80$  mg will be counted as high intensity, while simvastatin  $\leq 80$  mg and  $\geq 20$  mg will be counted as moderate intensity.

- o Statin therapies by name and dose
- Glucose lowering treatments (insulin and other)used at baseline, Week 12 and Week 24 will be summarized by treatment group, pre-specified category and standardized medication name. The tables will be sorted by decreasing frequency of standardized medication name within category based on the overall incidence across treatment groups at baseline and on the incidence in the alirocumab group at Week 12 and Week 24. Prespecified categories are:
  - o Insulins:
    - Fast acting
    - Intermediate (excluding premix)
    - Long acting
    - Inhaled
    - Premixed
  - Other glucose lowering treatments (non-insulin):
    - Biguanides
    - Sulfonylureas
    - Sulfonamides
    - Alpha glucosidase inhibitors
    - Thiazolidinediones
    - DPP-4 inhibitors
    - SGLT2 inhibitors
    - GLP-1 receptor agonists
    - Other blood glucose lowering drugs

The number of glucose lowering treatments (see Section 2.1.9) will also be described as quantitative and qualitative variables: 1, 2 and  $\ge 3$ .

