## Subgroups of interest are:

- Gender: Female, Male;
- Menopausal status, for female only: Yes, No;
  - For post-menopausal women, type of hormone replacement therapy: estrogen only, estrogen and progesterone, no estrogen or progesterone;
- Age: <65, [65 75[ and  $\ge 75$  years; 65,  $\ge 65$  years old;
- BMI: <25, [25-30],  $\ge 30$  in kg/m2;
- Race: White/Caucasian, non-White/Caucasian;
- Ethnicity: Hispanic or Latino, non-Hispanic or Latino, Not reported/Unknown;
- Region (North America, Europe, Rest of World);
- Duration of diabetes: <5, [5-10], >10 years, if the number of patients by subgroup are sufficient; otherwise by tertiles;
  - o Patients with duration of diabetes < 1 year are excluded.
- Prior history of myocardial infarction (silent or acute) or ischemic stroke: Yes, No;
- CKD: Yes, No, from cardiovascular medical history e-CRF page;
- ASCVD as per protocol (see Section 2.1.1): Yes, No;
- ASCVD including TIA (see Section 2.1.1): Yes, No;
- eGFR: <30,[30 60[, [60 90[,  $\ge$ 90 mL/min/1.73m^2, if there are not enough patients with eGFR <30, the <30 and the [30-60] categories will be pooled together;
- Baseline albumin/creatinine ratio: <30, [30 300[,  $\ge 300$  mg/g (<3.39, [3.39-33.9[,  $\ge 33.9$  mg/mmol);
- Diabetic kidney disease by category (cf Appendix C)
  - o Category 1: (G1A1, G2A1)

26-Apr-2017

- o Category 2: (G1A2, G2A2, G3aA1)
- o Category 3: (G1A3, G2A3, G3aA2, G3bA1)
- o Category 4: (G3aA3, G3bA2, G3bA3, G4A1, G4A2)
- o Category 5: (G4A3, G5A1, G5A2, G5A3)

If the numbers of patients by subgroup don't allow this subgroup analysis, other groupings will be explored.

- Baseline total PCSK9 level: <median, ≥median;
- Baseline free PCSK9 level: <median, ≥median;

- Baseline HbA1C:
  - $\circ$  <7, [7 − 9[, ≥9%. if the number of patients by subgroup meets the requirement (cf. above); otherwise <median, ≥median and by tertiles;
  - o Controlled DM (HbA1C<7%) vs uncontrolled DM (HbA1C≥7%)
- Statin treatment at randomization:
  - o Any statin versus no statin
  - o High intensity statin versus medium or low intensity statin at randomization
- Baseline non-HDL-C: <130, [130 160[, [160 190[,  $\ge 190$  mg/dL (<3.37, [3.37 4.14[, [4.14 4.91[,  $\ge 4.91$  mmol/L), ), if the number of patients by subgroup meets the requirement (cf. above); otherwise one of the following groupings will be explored:
  - $\circ$  <130, [130-160],  $\geq$ 160 mg/dL (<3.37, [3.37 4.14],  $\geq$ 4.14 mmol/L)

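### The SAP's statin-intensity table puts one pravastatin range in two classes, contradicts its own 30 mg example and gives most higher doses no class

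*SAP*

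**What the plan says.** SAP 2.4.2, under lipid-modifying therapy at randomization, plans to report "Proportion of patients according to highest intensity of statin therapies (high intensity, moderate intensity, low intensity) according to the following table". The table has three columns. Pravastatin appears in two of them, moderate and low, each time as "Pravastatin 10-20 mg". It has no entry in the high column.

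Three rules deal with doses that the table does not list:

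- Between classes: "A statin dose that falls in between two intensity classes will be counted in the class of lowest intensity". One of its two examples is that "pravastatin 30 mg will be counted as low intensity".
- Below the table: "A statin dose under the lower threshold of low intensity will be counted as low intensity".
- Above the table: "A statin dose above the higher threshold of high intensity will be counted as high intensity".

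The same section then asks for statin therapies to be listed by name and dose. SAP 2.4.4.1.3 includes, among the subgroups for the primary endpoint, "High intensity statin versus medium or low intensity statin at randomization". The SAP gives no other definition of statin intensity, so the table in 2.4.2 presumably defines these groups too.

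**The concern.** A coding table should give each recorded dose one class. Here the same range sits in two columns, and the SAP's own illustration of the between-classes rule treats 30 mg as lying in a gap that the printed ranges do not contain. Two programmers following the text could code the same patient differently, and neither could code 40 mg of pravastatin from the text at all.

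What is at stake is how background therapy is described. The trial enrolls patients on maximally tolerated statin and allows lower doses for several reasons (protocol 7.1, I 01), so readers will look at the intensity split to see how intensive the background treatment was. The statin-intensity subgroup also needs a definite class for every statin user.

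**Working it through.** No sample-size or error-rate arithmetic applies. The check is to apply the printed ranges and the three rules mechanically, starting with the SAP's own examples.

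**Inputs (SAP 2.4.2).** Pravastatin: moderate 10-20 mg, low 10-20 mg, high none. Atorvastatin: high 40-80 mg, moderate 10-20 mg. Lovastatin: moderate 40 mg, low 20 mg. Rosuvastatin: high 20-40 mg, moderate 5-10 mg.

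**Step 1: the SAP's worked examples.**

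| Example | Derivation from table and rules | SAP states | Reproduced? |
|---|---|---|---|
| Atorvastatin 30 mg | 20 < 30 < 40, so between moderate and high; the lower is moderate | moderate | yes |
| Lovastatin 10 mg | 10 < 20, so below the low threshold | low | yes |
| Rosuvastatin 80 mg | 80 > 40, so above the high threshold | high | yes |
| Pravastatin 30 mg | both ranges end at 20, so 30 lies between nothing, and there is no high threshold | low | no |

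Three of the four examples follow from the table. Only the pravastatin one does not.

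**Step 2: pravastatin dose by dose, as printed.**

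| Dose | What applies | Class |
|---|---|---|
| 5 mg | below the low threshold | low |
| 10 mg, 20 mg | two table cells | moderate and low |
| 30 mg | no cell and no rule; the example alone | low, by the example |
| 40, 60, 80 mg | no cell; not between classes; no high threshold to exceed | none |

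**Step 3: what the example implies.** For 30 mg to fall between two classes, the low range must end below 30 mg (it ends at 20) and the moderate range must start above 30 mg. Assumed lower bounds for the moderate range give:

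- 20, 25 or 30 mg: 30 mg is moderate, so the example fails.
- 31 or 40 mg: 30 mg lies in the gap and is low, so the example holds, and 10-20 mg is low only.

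The upper end matters separately. If the moderate range stopped at 40 mg, 80 mg would still have no class; if it ran to 80 mg, 80 mg would be moderate. The documents settle neither bound. They imply only that the range starts above 30 mg.

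**Step 4: where the coding is used.**

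- Descriptive intensity summary (SAP 2.4.2): both the overlap and the gap matter.
- High versus medium or low subgroup (SAP 2.4.4.1.3): moderate and low are pooled, so 10-20 mg falls on the same side whichever cell is used. Only the unclassed higher doses can be dropped or assigned ad hoc.
- Primary MMRM (SAP 2.4.4.1.1): its terms are treatment, stratum, time point, baseline non-HDL-C and interactions. There is no statin-intensity term.
- Eligibility (protocol 7.1, I 01): this rests on the Investigator's judgment of the highest tolerated dose and does not refer to the table.

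**The case against.** The best defence is that this is one mistyped cell in a descriptive table and that little depends on it. Much of that stands. The listing by statin name and dose will show the actual pravastatin doses whatever label they carry. Whether patients take the maximum dose, and their reasons for a lower one, are summarized separately (SAP 2.1.1). The subgroup pools the two classes that overlap, and the significance of its interaction term is given for descriptive purposes only.

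A fault in reading the PDF cannot be fully excluded. The simvastatin line after the rules, which as read puts 80 mg on both sides of the moderate/high boundary, may be such an artefact. But a whole duplicated cell is an unlikely reading error: the drugs in both columns are in alphabetical order, and the other three examples work.

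Stronger readings are tempting, and the documents do not support them:

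- A reader might infer that low-intensity patients are moved up, because the summary is by highest intensity. That phrase may simply choose among a patient's several statin records, and the between-classes rule leans the other way, to the lower class. The class is undetermined; no direction of error is shown.
- A reader might infer that every pravastatin user is affected. Doses under 10 mg resolve by rule, and 30 mg resolves by the example.
- A reader might infer that unclassed doses would end up in the high group. No rule sends them there, since pravastatin has no high threshold.
- A reader might infer that the definition of the trial population is compromised. Eligibility does not use the table.

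What the defence does not answer is that a final SAP gives a coding rule that cannot be applied as printed to 10-20 mg or to most doses above 20 mg.

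**Conclusion.** The point holds as an internal inconsistency of minor weight. The duplicate entry and the 30 mg example cannot both be right. Pravastatin 10-20 mg has two classes, and doses above 20 mg other than 30 mg have none.

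The consequences are limited to the statin-intensity summary at randomization and to possible loss or arbitrary placement of higher pravastatin doses in one subgroup analysis. The primary result is unaffected. The documents give no count or share of pravastatin users, so the number of patients involved cannot be stated. The conclusion assumes that the table was read correctly from the PDF, and the subgroup part also assumes that the subgroup uses this table.

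**What to change.** In SAP 2.4.2:

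1. Keep pravastatin 10-20 mg in the low column only.
2. Have the sponsor state the intended moderate range for pravastatin. It must start above 30 mg if the 30 mg example is to stand; the documents do not give the range, and none is proposed here.
3. Add a rule that a dose above the top listed range of a statin with no high-intensity entry takes one stated class.
4. Run every recorded statin and dose through the revised table and confirm that each gets exactly one class. As printed, lovastatin above 40 mg and atorvastatin below 10 mg also have none. Check the simvastatin 80 mg line against the source file at the same time.
5. State in SAP 2.4.4.1.3 that the subgroup uses this classification.

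The cost is one table cell, one added rule, one cross-reference and a small change to the coding program. No new data are needed.

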#### 2.4.2.1 Additional analyses of prior or concomitant medications

Additional analyses of selected concomitant medications will also be replicated in the subgroup of patients of the region North America, overall and in the fenofibrate stratum as per IVRS.

# 2.4.3 Extent of investigational medicinal product exposure and compliance

The extent of IMP exposure and compliance will be assessed and summarized by actual treatment received within the safety population (Section 2.3.2).

For alirocumab arm, dates of injection are retrieved from e-CRF 'Alirocumab Administration'. For usual care arm (except when no LMT other than statin is prescribed), dates of administration are retrieved from e-CRF 'Usual Care Medication for Lipid Modification therapy'.

# 2.4.3.1 Extent of investigational medicinal product exposure

#### Alirocumab arm

The extent of alirocumab exposure will be assessed by:

- the duration of alirocumab exposure in weeks defined as: (date of last open-label alirocumab injection date of first open-label alirocumab injection + 14 days) / 7, regardless of unplanned intermittent discontinuations (see Section 2.5.2 for calculation in case of missing or incomplete data)
- the total number of injections by patient
- the number and percentage of patients with an up-titration; (patients with an up-titration are defined as up-titrated patients according to IVRS/IWRS Week 12 transaction with at least 1 injection of alirocumab 150 mg afterwards).

# Usual care arm (except when no LMT other than statin is prescribed)

The extent of usual care treatments will be assessed by:

• The duration of exposure in weeks defined as: (last dose of open-label treatment date – first dose of open-label treatment date + 1 day) / 7, regardless of unplanned intermittent discontinuations (see Section 2.4.3 for calculation in case of missing or incomplete data)

All quantitative parameters above will be summarized using number, mean, SD, median, Q1 and Q3, minimum, and maximum (non-integer values will be rounded to 1 decimal place). In addition, duration of treatment exposure will be summarized and presented graphically using bar chart displaying the percentage of patients according to the following categories:  $\geq 1$  day to <4 weeks,  $\geq 4$  weeks to <8 weeks,  $\geq 8$  weeks to <12 weeks,  $\geq 12$  weeks to <16 weeks,  $\geq 16$  weeks to <24 weeks, and  $\geq 24$  weeks.

### 2.4.3.2 Compliance

A given administration will be considered noncompliant if the patient did not take the planned dose of treatment as required by the protocol. No imputation will be made for patients with missing or incomplete data.

### Alirocumab arm

Compliance will be assessed using the following parameters:

- the mean injection frequency, defined for each patient as the average number of days between 2 injections, that is: (last injection date first injection date) / (number of injections 1) for patients receiving at least 2 injections
- the overall compliance for injections, defined for each patient as: (number of injections performed during the study period / number of theoretical injections to be performed during the study period)\*100.

26-Apr-2017

O Number of theoretical injections will be defined for each patient as: [(last injection date – first injection date) / 14] + 1

These parameters will be summarized descriptively (N, mean, SD, median, Q1 and Q3, minimum, and maximum). Percentage of patients with overall compliance <80% and  $\ge80\%$  will be presented.

- Percentage of patients who discontinued temporarily in relation with an AE will be presented.
  - For patients with temporary discontinuation, the number of injections not performed will be presented by category: 1 injection, 2 injections, 3 or more injections.

Cases of symptomatic overdose with IMP (i.e., an event that is suspected by the Investigator or spontaneously notified by the patient (not based on systematic injection counts), and defined as at least twice of the intended dose within the intended therapeutic interval (i.e. 2 or more injections are administered in <7 calendar days) will be specified as an AESI and will be listed and described as such in the AE analysis (see Section 2.1.4.1).

## Usual care arm (except when no LMT other than statin is prescribed)

The compliance is defined by the number of days with all intakes as planned / duration of exposure x 100. The number of days with all intakes as planned will be obtained by subtracting the total number of days with at least one dose missed (from the Compliance e-CRF forms) from the duration of exposure. The compliance will be summarized descriptively (N, mean, SD, median, Q1 and Q3, minimum, and maximum) and percentage of patients with compliance <80% and ≥80% will be presented.

- Percentage of patients who discontinued temporarily in relation with an AE will be described.
  - o For patients with temporarily discontinuation, the number of days without treatment will be presented.

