## 6 STUDY DESIGN

#### 6.1 DESCRIPTION OF THE PROTOCOL

This is a Phase 3b/4 randomized, open-label, parallel group study to assess the efficacy and safety of alirocumab administered by subcutaneous (SC) injection versus usual care in patients with Type 2 diabetes and mixed dyslipidemia at high CV risk with non-HDL-C not adequately controlled with maximally tolerated statin therapy. The study will be multinational and multicenter. The study consists of a screening period of up to 3 weeks, an open-label treatment period (OLTP) of 24 weeks, and a safety observation period of 8 weeks.

Patients, unless they are statin intolerant, will be taking a stable, maximally tolerated dose of statin therapy without other lipid modifying therapies (LMT). Statin dose and dose regimen should be stable throughout the entire study duration including for 4 weeks prior to the screening period and from screening to the end of the open label treatment period. Patients should continue to follow a cholesterol lowering diet during the study, however, the Investigator may reinforce diet recommendations according to local/regional guidelines. Patients should be receiving treatment for diabetes in accordance with local/regional standards of care. Changes to antihyperglycemics should be limited and made only in circumstances where it is clinically needed.

Randomization will be unbalanced (2:1, alirocumab:usual care).

The usual care arm includes the option to continue on the maximum dose of statin that is tolerated by the patient without the addition of a new LMT at randomization, or may initiate either ezetimibe, fenofibrate, omega-3 fatty acids, or nicotinic acid at randomization for the remainder of the 24-week treatment period. Initiation of usual care treatment (IMP) should start as soon as possible after randomization, but no later than 7 days from the day of randomization.

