## 11.4.1.1 Extent of investigational medicinal product exposure

#### Alirocumab arm

The total exposure will be assessed by:

Duration of alirocumab exposure in weeks is defined as: (last dose of open-label treatment date - first dose of open-label treatment date + 14 days)/7, regardless of unplanned intermittent discontinuations.

The total number of injections by patient.

The number (n) and percentage (%) of patients with an up-titration in the alirocumab group will be described.

Usual care arm (except when no LMT other than statin is prescribed)

The total duration of exposure in weeks is defined as: (last dose of open-label treatment date - first dose of open-label treatment date + 1 day)/7, regardless of unplanned intermittent discontinuations.

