## **11.4.1.2 Compliance**

A given administration will be considered noncompliant if the patient did not take the planned dose of treatment as required by the protocol. No imputation will be made for patients with missing or incomplete data.

Compliance will be assessed using the following parameters:

- For alirocumab:
  - the injection frequency will be defined for each patient as the average number of days between 2 injections, that is: (last dose date first dose date)/(number of injections -1).
  - The compliance is defined by the actual number of injections/number of planned injections
- For IMPs in usual care:
  - the compliance is defined by the number of days with all intakes as planned / duration of exposure x 100. The number of patients with a compliance ≥80% will also be assessed.

These parameters will be summarized descriptively (N, Mean, SD, Median, Min and Max).

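### Usual-care compliance subtracts missed days from, and divides by, an exposure defined in weeks, so the 80% split goes wrong if programmed as written

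*SAP*

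**What the plan says.** **SAP 2.4.3.1, usual-care arm.** The measure is introduced as "The duration of exposure in weeks defined as", and the formula is the last dose date minus "first dose of open-label treatment date + 1 day) / 7". Its unit is therefore weeks.

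**SAP 2.4.3.2, usual-care arm.** "The compliance is defined by the number of days with all intakes as planned / duration of exposure x 100". The count of days with all intakes is obtained by "subtracting the total number of days with at least one dose missed (from the Compliance e-CRF forms) from the duration of exposure". The result is summarised descriptively, and patients are split at 80%.

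**Protocol 11.4.1.1 and 11.4.1.2.** The exposure definition is the same: "The total duration of exposure in weeks is defined as", again with a division by 7. The ratio is also the same: "the compliance is defined by the number of days with all intakes as planned / duration of exposure x 100". The Protocol plans to count patients at 80% or more, but does not say how the number of fully dosed days is obtained.

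Neither document defines a usual-care exposure in days or gives a conversion. SAP 1.5 and 1.6 record no statistical modifications. The alirocumab measure in SAP 2.4.3.2 is not affected: it divides injections given by theoretical injections, so its units agree.

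**The concern.** The compliance rule uses a term that has one definition, and that definition is in the wrong unit for the rule. In the SAP version each missed day is set against a total of about 24 instead of about 168. A patient who missed a handful of doses in half a year would then be tabulated below 80%.

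What is at stake is the description of how well the comparator was taken. The trial is open-label, and the usual-care arm, including the fenofibrate stratum, is the reference for both tested comparisons. A reader will look at the 80% split to see whether those drugs were taken as prescribed. The alirocumab split has no such fault, so the two arms would be described by measures that are not comparable.

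**Working it through.** **Inputs**
- Planned usual-care treatment: 24 weeks, that is 168 days (Protocol 6.1).
- Exposure in weeks: (last dose date - first dose date + 1) / 7 (SAP 2.4.3.1).
- Compliance numerator: exposure minus days with a missed dose (SAP 2.4.3.2).
- Cut: 80% (SAP 2.4.3.2).

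**Exposure formula against the planned duration.** First dose on Day 1 and last dose on Day 168: (168 - 1 + 1) / 7 = 24.0 weeks. The formula reproduces the plan's 24 weeks.

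**Compliance with m missed days, 168-day exposure**
- As written: 100 x (24 - m) / 24
- In days: 100 x (168 - m) / 168

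| Missed days m | As written | In days |
|---|---|---|
| 0 | 100.0% | 100.0% |
| 1 | 95.8% | 99.4% |
| 4 | 83.3% | 97.6% |
| 5 | 79.2% | 97.0% |
| 10 | 58.3% | 94.0% |
| 24 | 0.0% | 85.7% |
| 25 | -4.2% | 85.1% |
| 33 | -37.5% | 80.4% |
| 34 | -41.7% | 79.8% |

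The shortfall from 100% is m/24 as written and m/168 in days, so the literal rule multiplies it by 168/24 = 7.

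**Who is misclassified.** As written, a patient falls below 80% when m exceeds 0.2 x 24 = 4.8, that is from 5 missed days. In days this happens when m exceeds 0.2 x 168 = 33.6, that is from 34. Patients with 5 to 33 missed days are on the wrong side of the cut.

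**Other exposure lengths.** For 158 days (22.57 weeks) the literal rule flags from 5 missed days and the correct one from 32. For 172 days (24.57 weeks) the figures are 5 and 35.

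**Protocol version.** If fully dosed days are counted directly and divided by weeks, full adherence gives 100 x 168 / 24 = 700%. The 80% mark is then passed with 20 fully dosed days (20/24 = 83.3%), so this version overstates compliance.

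**The case against.** The strongest reply is that the intent is plain. The SAP calls the numerator a number of days, and subtracting days from exposure to obtain days makes sense only if exposure is in days. The formula in SAP 2.4.3.1 already holds that day count before it divides by 7. Negative percentages or 700% would be caught in any check of the output.

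Most of this stands: days were meant, and a programmer may well convert unprompted. But not every wrong value looks wrong. For a 24-week exposure the literal SAP rule turns negative only from 25 missed days; 79.2% and 58.3% are believable figures and would pass a plausibility check.

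It also stands that compliance is descriptive. It does not define the ITT or safety population (SAP 2.3), and the treatment-change sensitivity analysis (SAP 2.4.4.1.3) uses permanent discontinuation or an added lipid therapy, not the 80% split.

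A reader might infer more than the documents support:
- *That fully adherent completers would be reported as non-compliant.* They would not. With m = 0 the SAP ratio is 100% in either unit, and a late start does not change this because the denominator is the patient's own exposure.
- *That the exposure categories are also faulty*, because the top one starts at exactly 24 weeks while usual care may begin "no later than 7 days from the day of randomization" and the Week 24 visit may be 3 days early. A patient treated from Day 8 to Day 166 has (166 - 8 + 1) / 7 = 22.7 weeks. That is truly below 24, and the categories do not claim to measure adherence. Completion and discontinuation are reported separately (SAP 2.2), and exposure is also summarised as a continuous variable. Nor is a bias against usual care shown. With the last dose on the visit day, 41 of 56 permitted start and visit dates give less than 24 weeks for usual care, but only 2 of 7 if all start on Day 1, against 3 of 7 injection dates for alirocumab. The direction depends on the assumed start day, and these are counts of dates, not patient rates.
- *That the top category should start at 22 weeks.* An alirocumab patient last injected on Day 141, who missed the Week 22 injection, has (141 - 1 + 14) / 7 = 22.0 weeks and would join the completers.

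**Conclusion.** The unit mismatch is real and stands in both documents. Followed literally, the SAP rule puts usual-care patients with about 5 to 33 missed days in a 24-week exposure below 80%, although they took 80.4% to 97.0% of days as planned. The Protocol ratio errs in the opposite direction.

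This rests on two assumptions: an exposure near 168 days, and programming without a conversion from weeks to days. The documents do not show how many patients fall in that range, so no rate of misclassification can be given. The consequence is limited to a descriptive table in one arm; the primary and key secondary tests are untouched. This is a minor point, worth correcting because it costs almost nothing. The exposure categories need no change.

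**What to change.** In SAP 2.4.3.2, define usual-care compliance as 100 x (exposure in days - days with at least one missed dose) / exposure in days, where exposure in days = last dose date - first dose date + 1. SAP 2.4.3.1 can keep weeks for the exposure summary. Record the clarification in SAP 1.6, since Protocol 11.4.1.2 has the same ambiguity.

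The cost is one phrase of SAP wording and one line in the modifications section. No new data or analyses are needed.
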